3.3 Measurement Definitions

3.3.1 TMS Measures

Transcranial magnetic stimulation (TMS) is a neurophysiologic test for assessing upper motor neuron function. A magnetic coil is positioned on the head above the motor cortex at a location that causes excitation of the abductor pollicis brevis (APB) muscle in a participant's dominant hand. High-frequency sampling of motor evoked potentials (MEP) in the APB is used to record neurophysiologic response to specific magnetic field strengths and sequences. The MEP traces are used to calculate a range of derived measures. MEPs that were below the limit of detect and recorded as zero mV were replaced by 0.005 mV.

- Resting motor threshold (RMT): RMT is the magnetic field strength, measured as a percentage of the maximum stimulator output, that produces at least a 0.05 mV response in at least 5 of 10 consecutive trials.

- Maximum MEP amplitude: Maximum MEP amplitude is defined as the maximum MEP elicited as a percentage of the maximum CMAP.
- Input/Output curve parameters: MEPs elicited by stimuli ranging in strength from 60% of RMT to 150% of RMT follow a sigmoidal curve with upper and lower thresholds and a smooth, symmetric transition between the thresholds. A four-parameter logistic function fit to the input/output curve after log-transformation of output potentials yields estimates of maximum amplitude, minimum amplitude, midpoint of activation, and slope at the midpoint of activation.
- Cortical silent period (CSP): CSP is the suppression of voluntary muscle contraction elicited by stimulation equal to 120% of RMT. CSP duration is measured from the time of the muscle activity suppression to return of muscle activity.
- Short-interval intracortical inhibition (SICI): Paired-pulse SICI is defined as the ratio of the response after a conditioning pulse equal to 80% of RMT is administered 3 ms prior to the signaling pulse divided by MEP amplitude. SICI is calculated as the geometric mean of replicate estimates.
- Intracortical facilitation (ICF): Paired-pulse ICF is defined as the ratio of the response after a conditioning pulse equal to 80% of RMT is administered 15 ms prior to the signaling pulse divided by MEP amplitude. ICF is calculated as the geometric mean of replicate estimates.

TMS tracings are centrally reviewed and processed. The central reader indicates the reliability of the overall TMS assessment and of individual measures using a set of quality flags:

- Overall quality: (0) poor quality, (1) acceptable quality, (2) raw data has no traces
- RMT estimation: (-1) RMT is missing, (0) poor quality estimate of RMT, (1) acceptable quality estimate of RMT, (2) RMT is greater than 100% of maximum stimulator output
- Input/Output curve estimation: (-1) no input/output traces obtained, (0) poor quality, (1) acceptable quality
- CSP estimation: (-1) no CSP traces obtained, (0) poor quality, (1) acceptable quality, (3) acceptable quality

TMS assessments that were evaluated as of acceptable quality overall and of acceptable quality for each category of measurement are used for primary analysis.

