13.6. Analysis of Primary Outcome Measure

The effect of mexiletine on RMT will be estimated from a modified intention-to-treat sample (all participants receiving at least one dose of study drug, classified according to randomization) using a shared-baseline repeated-measures two-way ANOVA with fixed effects of visit (4 levels) and treatment x post-baseline visit interaction ($2 \times 2 = 4$ levels) and unstructured covariance among repeated measures (10 terms). Use of a shared baseline reflects the true state of the sample prior to randomization and has the benefit of adjusting for chance baseline differences in RMT across the three treatment groups and improved power similar to ANCOVA. Treatment-dependent differences in the 4-week change in RMT and any sustained benefit at 8 weeks will be estimated using linear contrasts of the least-square means. Not knowing whether a linear dose effect will be present, the primary test will compare each active arm to placebo, using Dunnett's method to control for multiple comparisons. A secondary analysis will test for linear dose response. The proposed mixed effects model makes efficient use of observed data and is unbiased in the presence of loss to follow-up if the probability of loss to follow-up is predictable from observed RMT results. Additional covariates may be included in the primary analysis if rates of loss to follow-up are higher among participants randomized to mexiletine. Wilcoxon rank sum tests of changes from baseline for each active arm vs. placebo and each follow-up time point, imputing the worst observed outcome for missing data, will be evaluated as a sensitivity analysis. The final primary model will be specified prior to unblinding. An additional secondary analysis will look at the effect of mexiletine dosing as achieved, using the estimated serum mexiletine level in place of treatment group. Subgroup differences will be tested by including subgroup, subgroup x visit, and subgroup x treatment x post-baseline visit terms. Subgroups of interest will be pre-specified prior to unblinding.

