This Statistical Analysis Plan (SAP) defines the outcome measures and analysis samples and specifies the planned analyses of data from [name] Mexiletine II trial. This SAP is specific to analysis of data related to the ALS participants in the randomized intervention trial. The SAP supplements the clinical protocol. Please refer to the clinical protocol for details on the rationale for the intervention, eligibility criteria, conduct of the trial, clinical assessments and the timing of their use in the trial, definitions and reporting of adverse events, data management conventions, and regulatory oversight and compliance procedures. In case of discrepancies between the SAP and the clinical protocol concerning matters of analysis, the SAP is authoritative. On all other matters, the clinical protocol is authoritative.

2. Study Design

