3.4 Determination of Sample Size

[name] (personal communication) reports a mean 4-week change in RMT among 18 ALS patients of 6.2% and a SD of 5.1%. A sample size of 60 participants randomized 1:1:1 with up to 10% loss to follow-up would provide 80% power to detect an effect of a given dose of mexiletine on RMT if the increase in RMT relative to placebo is at least 5.3% based on a simple one-way ANOVA and two-sided alpha = 0.027 for each of the two active arms. This estimate of power is conservative relative to our proposed shared-baseline mixed model analysis. This effect is roughly 85% of the natural variation in RMT over 4 weeks. Power will also be greater if a linear dose-response is present, with 80% power to detect a slope of 2.4% / 300 mg dose. Selection of the active dose exhibiting greater increase in RMT in our sample, irrespective of compliance with assigned dose and thus reflecting variation in tolerance, will correctly identify the dose with greater true ITT efficacy with at least 80% probability if the difference in efficacy is at least 1.4%.

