3.7.7 Missing Data

The planned mixed model yields estimates that are unbiased conditional on the observed scores under a missing at random assumption. Sensitivity analyses may be pursued to impute missing values or otherwise construct models for unobserved outcomes if more than 20% of participants are missing follow-up data for any reason.

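### SAP 3.3.1 gives RMT readings above 100% of stimulator output no rule and, read literally, drops them because of their own value; the likely effect is small, but one firm sensitivity analysis should keep them.

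*SAP*

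**What the plan says.** SAP 3.3.1 measures RMT as a percentage of maximum stimulator output, so 100 is the highest measurable value. The central reader gives RMT one of four codes: -1 for missing, 0 for poor, 1 for acceptable, and "2) RMT is greater than 100% of maximum stimulator output". The inclusion rule follows: "TMS assessments that were evaluated as of acceptable quality overall and of acceptable quality for each category of measurement are used for primary analysis". No section gives code 2 a value, a rank or a censoring rule. A detection-limit rule exists only for motor evoked potentials, where zero becomes 0.005 mV.

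SAP 3.7.7 calls the mixed-model estimates "unbiased conditional on the observed scores under a missing at random assumption". It adds that sensitivity analyses may be pursued "if more than 20% of participants are missing follow-up data for any reason". SAP 3.7.2 lists dose and washout contrasts only.

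Protocol 13.6 plans a Wilcoxon sensitivity analysis, "imputing the worst observed outcome for missing data". Protocol 13.4 promises non-ignorable-missingness analyses if loss to follow-up appears related to arm. The SAP repeats neither, and where the two documents differ, "concerning matters of analysis, the SAP is authoritative".

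On direction, Protocol 4.1 and the sample-size text (Protocol 13.9, SAP 3.4) expect mexiletine to raise RMT. SAP 3.7.1 names a fall in RMT relative to placebo as the evidence of efficacy, and the 600 vs 300 mg/day comparison in SAP 3.7.2 also speaks of reducing RMT.

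**The concern.** A code 2 result is not a failed test. It tells the analyst that RMT exceeds 100. If only code 1 is admitted, the reading leaves the primary analysis because of the value it would have had. If the drug raises RMT, more readings leave the active arms than placebo, and those that leave are the highest. Missing at random does not strictly hold for such a loss. The pre-treatment RMTs in the model limit the bias but do not remove it.

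At stake are a slight understatement of the effect and a loss of transparency. After a null result, a reader could not tell how many top-of-scale values were set aside, or from which arm, and nothing firmly planned in the SAP would show whether it mattered.

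**Working it through.** **Inputs from the documents (SAP 3.4):** SD of 4-week change 5.1; effect 5.3; 60 patients randomised 1:1:1 with 10% loss, so 18 evaluable per arm (18 placebo, 36 active); alpha 0.027 per dose.

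**The plan's own figure.** Standard error = 5.1 × √(2/18) = 1.70, and 5.3/1.70 = 3.12. Power is 79.7% by noncentral t with 51 df (81.8% by the normal approximation), so the stated 80% reproduces. It allows for loss to follow-up but not for code 2.

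**Assumptions.** The documents give no RMT level. I took baseline means of 60, 65 and 70, total SD 15, and a slope SD of 2 per month. The residual SD is then √((5.1² − 2²)/2) = 3.32, so that the 4-week change has SD 5.1. An RMT of at most 100 is required at screening, because Protocol 5.2.1 requires an obtainable threshold. The main case has no drift: SAP 3.4 says "This effect is roughly 85% of the natural variation in RMT over 4 weeks", and 5.3/6.2 = 85%, so the plan treats the 6.2 as variation.

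**Loss and attenuation at Week 4 (true effect 5.3).** The mixed model is the SAP 3.7.1 model fitted to 300,000 simulated patients per scenario. The regression adjusts for mean pre-treatment RMT.

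| Baseline mean | Lost, placebo | Lost, active | Expected lost of 54 | Mixed model | Regression |
|---|---|---|---|---|---|
| 60 | 0.2% | 0.7% | 18 × 0.002 + 36 × 0.007 = 0.3 | 5.28 | 5.27 |
| 65 | 0.4% | 1.6% | 18 × 0.004 + 36 × 0.016 = 0.6 | 5.27 | 5.24 |
| 70 | 0.8% | 3.1% | 18 × 0.008 + 36 × 0.031 = 1.3 | 5.25 | 5.20 |

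Attenuation at mean 70 is 1 − 5.25/5.30 = 0.9% (mixed model) or 1 − 5.20/5.30 = 1.9% (regression). The Monte Carlo standard error of the mixed-model figures is about 0.018, so 5.28 is hardly distinguishable from 5.30. A coarser simulation adds the change SD of 5.1 on top of a baseline SD of 15, so more readings cross 100. At mean 70 it gives 5.20 against 5.34 with all values, or 2.6%.

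**Type I error and direction.** With no drug effect, both arms lose the same share and the estimate stays at zero. In the coarser simulation at mean 70 the rejection rate is 5.3% with exclusion and 5.5% without. With an effect of −5.3 at mean 70 the mixed model gives −5.29, again towards zero.

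**Power.** For pooled active vs placebo at alpha 0.05, adjusted for pre-treatment RMT, power is 98% with all values and 97–98% with exclusion at means 60 to 70. This is a different comparison from the per-dose 80%.

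**The 20% trigger.** Missing share = 1 − 0.9 × (1 − code 2 share). Passing 20% needs a code 2 share above 1 − 0.8/0.9 = 11.1%. At means 60 and 70 the total is 10.5% and 12.1%, so the optional analysis would not be triggered.

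**The protocol's Wilcoxon.** If code 2 counted as missing, the highest RMTs would be scored as the worst outcome on the protocol's direction. For one dose vs placebo (18 vs 18, alpha 0.027), power with code 2 ranked highest vs imputed worst is 86% vs 84% at mean 60 and 85% vs 77% at mean 70.

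**The case against.** The best reply is that this concerns about one reading, and that the analyst would handle it sensibly. The size is indeed small. The SAP also never says in terms that code 2 is dropped; that follows only from applying its inclusion sentence literally. SAP 3.1.2 reports numbers of subjects, so gaps would be visible, though not their cause.

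A reader might infer more in four ways, and the documents do not carry any of them.

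- **A larger bias.** An assumed drift of +6.2 gives 5.13 at mean 70 and 5.02 at mean 75 (3% and 5%), and 20.7% missing at mean 75. But SAP 3.4 treats 6.2 as variation. With that drift, 30% of placebo and 44% of active patients at mean 70 (42% and 56% at mean 75) would have an RMT above 100/1.2 = 83.3, beyond reach of a 120% pulse.
- **Every flag must pass before RMT counts.** SAP 3.3.1 has the reader rate individual measures, and SAP 3.3.2 gates TTNCS measures separately, so each flag most naturally gates its own measure. The 4–6% attenuation under the wider reading also needs the cortical silent period, "elicited by stimulation equal to 120% of RMT", to count as not obtained above 83.3. No section says so.
- **No firm sensitivity analysis exists anywhere.** Protocol 13.6 words its Wilcoxon firmly, and the SAP's silence is arguably not a discrepancy. What stands is narrower. The SAP carries over neither that test nor Protocol 13.4. Protocol 13.4 concerns loss to follow-up, and since code −1 already denotes missing, it is unclear whether code 2 counts as missing data at all.
- **The wrong direction invalidates the test.** The primary test is two-tailed, so the SAP's reference to a fall affects the success statement and the meaning of worst outcome, not the p-value.

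**Conclusion.** The gap is real and of low severity. Applied literally, SAP 3.3.1 makes an outcome-dependent exclusion on the primary endpoint, and no SAP analysis firmly keeps the excluded readings. For assumed baseline means of 60 to 70, SD 15 and no drift, the cost is about 0.3 to 1.3 readings among 54 patients and a 0 to 2% attenuation, without type I inflation and with almost no loss of power. The frequency cannot be derived from the documents, so these are illustrations. They do not support a claim that the primary conclusion is in danger. The conflict over the direction of benefit is a plain textual contradiction and does not depend on these assumptions.

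**What to change.** Before unblinding:

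- **SAP 3.3.1:** state that RMT code 2 is a valid result right-censored at 100, not a quality failure, and that 100 is not substituted. State that only the overall and RMT flags gate RMT, while the other flags gate their own measures.
- **SAP 3.7.2:** leave the primary mixed model unchanged, with code 2 entering as missing. Add one mandatory Week 4 sensitivity analysis that keeps code 2 whatever the amount of missing data. It can be a Tobit regression right-censored at 100, adjusted for the mean of the measurable pre-treatment RMTs, or a rank ANCOVA with code 2 at the highest rank, adjusted for pre-treatment rank. One of the two is enough.
- **Reporting:** give code 2 counts by arm and visit.
- **Wilcoxon:** if the Protocol 13.6 test is retained, rank code 2 as the highest RMT.
- **Direction:** reconcile the fall in RMT in SAP 3.7.1 and 3.7.2 with the rise in Protocol 4.1 and SAP 3.4, so that the evidence statement and any worst-outcome ranking agree.

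The cost is a few sentences and one short analysis, with no new data. The Tobit relies on the shape of the tail above 100. The rank analysis avoids that, but has about 93–94% power against 97–98% for the Tobit and gives no effect in RMT units.

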3.3.2 TTNCS Measures

Threshold-tracking nerve conduction studies (TTNCS) is a neurophysiologic test for assessing lower motor neuron function. The following measures were obtained using standard procedures (Kiernan et al. 2000): strength-duration measures of strength duration time-constant (SDTC) and rheobase; threshold electrotonus measures of depolarizing threshold electrotonus at 40 to 60 ms [TEd (40-60 ms)], 90 to 100 ms [TEd (90-100 ms)], and at peak [TEd (peak)] and hyperpolarizing threshold electrotonus at 10 to 20 ms [TEh (10-20 ms)] and 90 to 100 ms [TEh (90-100 ms)]; recovery cycle measures of RRP, superexcitability, subexcitability after first pre-pulse, and subexcitability after second pre-pulse; peak amplitude measures of compound motor evoked potential (CMAP) and stimulus for 50% maximum response.

TTNCS tracings are centrally reviewed and processed. A central reader indicates the reliability of the overall TTNCS assessment and of individual measures using a set of quality flags. For primary analysis, all measures were excluded if the overall quality flag indicated that the full assessment was unusable. Otherwise, acceptable quality for primary analysis was separately indicated for peak amplitude (CMAP, stimulus for 50% maximum response), strength-duration measures (SDTC, rheobase), threshold electrotonus (TEd (40-60 ms), TEd (90-100 ms), TEd (peak), TEh (10-20 ms), TEh (90-100 ms)), RRP, superexcitability, and subexcitability (after first and second pre-pulse).

3.3.3 ALSFRS-R

The ALSFRS-R (Cedarbaum et al. 1999) is a 12-item clinician-completed interview scale for assessing participants' function in four domains: bulbar, fine motor, gross motor, and respiratory. Each item is scored from 0 to 4 with higher scores indicating greater function. The ALSFRS-R total score is the sum of all items (range 0 to 48).

3.3.4 SVC

Slow vital capacity (SVC) is the maximum volume of air that can be slowly exhaled after slow, maximal inhalation. Trained technicians coach participants through 3 to 5 maneuvers using a spirometer. A minimum of 3 completed SVC maneuvers are required to calculate an estimate of maximum SVC for a given participant visit. The maximum volume expired is converted to percent of predicted normal. Normal values are calculated based on sex, age, and height using equations published by Knudsen et al. (1983).

3.3.5 APB Strength

Bilateral abductor pollicis brevis (APB) muscle strength will be measured quantitatively by hand-held dynamometry (HHD).

3.3.6 Cramping

Frequency of muscle cramping and maximum pain from muscle cramping is collected at baseline by retrospective report of the prior 7 and 30-day intervals. Prospective muscle cramping and pain from muscle cramping is recorded starting at baseline by participants in daily diaries and then summarized as weekly summaries of total number of cramps experienced and maximum and average daily maximum pain from muscle cramping.

3.3.7 Fasciculations

Data on muscle fasciculations are captured at baseline by retrospective report of the prior 14-day interval. Data are captured on the experience of any fasciculations, the average duration of fasciculations, the association of fasciculations with exertion or times of rest, the degree to which fasciculations interfere with daily activities, and interference of fasciculations with sleep. Prospective data on fasciculations are recorded starting at baseline by participants in daily diaries and then summarized as weekly summaries indicating the number of days with no fasciculations, with fasciculations after exertion that did not substantially interfere with daily activities, with fasciculations at rest or after exertion that did not substantially interfere with daily activities, and fasciculations that substantially interfered with daily activities.

3.3.8 RAND-36

The RAND-36 (Hays et al. 1993, 2001) is a 36-item, self-reported, generic profile, health-related quality of life instrument. Eight health domains are assessed: physical functioning (10 items), role limitations caused by physical health problems (4 items), role limitations caused by emotional problems (3 items), social functioning (2 items), emotional well-being (5 items), energy/fatigue (4 items), pain (2 items), and general health perceptions (5 items). An additional single item assesses change in perceived health during the last 12 months. Except for this single assessment of change during the last 12 months, the questions assess either current health or health over the previous 4 weeks. Each of the 35 items are transformed to a 0 to 100 range with 100 indicating maximal health, and items within a domain are averaged together. Two correlated physical and mental summary scores are derived from an oblique factor analysis. Higher scores indicate better health.

3.4 Determination of Sample Size

[name] (personal communication) reports a mean 4-week change in RMT among 18 ALS patients of 6.2% and a SD of 5.1%. A sample size of 60 participants randomized 1:1:1 with up to 10% loss to follow-up would provide 80% power to detect an effect of a given dose of mexiletine on RMT if the increase in RMT relative to placebo is at least 5.3% based on a simple one-way ANOVA and two-sided alpha = 0.027 for each of the two active arms. This estimate of power is conservative relative to our proposed shared-baseline mixed model analysis. This effect is roughly 85% of the natural variation in RMT over 4 weeks. Power will also be greater if a linear dose-response is present, with 80% power to detect a slope of 2.4% / 300 mg dose. Selection of the active dose exhibiting greater increase in RMT in our sample, irrespective of compliance with assigned dose and thus reflecting variation in tolerance, will correctly identify the dose with greater true ITT efficacy with at least 80% probability if the difference in efficacy is at least 1.4%.

3.5 Analysis Samples

The following analysis samples will be used for testing safety, tolerability, and efficacy endpoints:

- Safety and Tolerability (ST) Sample: ALS participants who are eligible, randomized, and take at least one dose of study drug, classified according to the actual treatment received. Observations made after premature permanent discontinuation of study drug are included in this sample, should such participants remain on study.
- Efficacy Modified Intent-to-treat (mITT) Sample: ALS participants who are eligible, randomized, and take at least one dose of study drug, classified according to their randomized treatment assignment. Observations made after premature permanent discontinuation of study drug are included in this sample, should such participants remain on study.

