13.3. Analysis Populations

The modified intent-to-treat (mITT) population will include all study subjects who are randomized and receive at least one dose of study drug. The mITT population will be used for all safety and tolerability analyses, with participants classified according to the treatment actually received. The mITT population will be used for primary efficacy analyses, with participants classified according to their randomized treatment assignment regardless of which treatment was actually received.

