2.3 Study Population

Individuals eligible for trial participation are men or women at least 18 years old who meet the El Escorial criteria of possible, laboratory-supported probable, probable, or definite criteria for a diagnosis of sporadic ALS received within 60 months of screening who have a slow vital capacity (SVC) at least 50% of that expected based on age, sex, and height, a measurable RMT of the abductor pollicis brevis (APB) by TMS, and a median nerve compound motor action potential (CMAP) by TTNCS of at least 1.5 mV. Detailed inclusion and exclusion criteria are specified in the clinical protocol.

Participants will be recruited from approximately 9 clinical sites located through the US that are part of the Northeast ALS (NEALS) Consortium.

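### SAP 3.5 adds an undefined condition, *eligible*, to both analysis samples; read literally, it could leave out a dosed participant whom protocol 13.3 includes

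*SAP*

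**What the plan says.** SAP 3.5 opens with "The following analysis samples will be used for testing safety, tolerability, and efficacy endpoints" and then gives two definitions, with no third sample:

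- "Safety and Tolerability (ST) Sample: ALS participants who are eligible, randomized, and take at least one dose of study drug", classified by treatment received.
- "Efficacy Modified Intent-to-treat (mITT) Sample: ALS participants who are eligible, randomized, and take at least one dose of study drug", classified by randomized arm.

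Protocol 13.3 has two conditions rather than three: "The modified intent-to-treat (mITT) population will include all study subjects who are randomized and receive at least one dose of study drug". It adds "The mITT population will be used for all safety and tolerability analyses" and uses the same population for primary efficacy. Protocol 13.6 describes the primary analysis sample as "all participants receiving at least one dose of study drug, classified according to randomization". Neither section mentions eligibility.

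The SAP's opening section says that the SAP prevails over the protocol where the two differ on analysis. SAP 3.2.3 and 3.2.4 take the ST sample as the denominator for the safety and tolerability proportions, and SAP 3.8.1 summarizes treatment-emergent adverse events in it.

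**The concern.** Under the precedence rule, the narrower SAP definition governs. Protocol 5.5 expects that some subjects may turn out, at any point, to have been enrolled in error, and it withdraws them from the study. It does not say that data already collected are set aside. Such a subject may already have taken mexiletine, for example if a history of arrhythmia or use of an excluded drug (protocol 5.2.2) comes to light late. On the literal wording of SAP 3.5, that person belongs to neither sample.

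Two things are at stake:

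- **Safety.** Adverse events in people who were exposed would be absent from the summary tables. Someone enrolled despite an exclusion that was set for safety is a person whose events a reader would particularly want to see.
- **Efficacy.** Participants could be removed after randomization, in some cases after outcome data exist. The protocol's mITT definition avoids this.

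SAP 3.9.1 (participant disposition) has no line for dosed participants left out of the samples, so an exclusion might not be visible in the report.

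**Working it through.** **The definitions side by side**

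| | Randomized | Dosed | Eligible |
|---|---|---|---|
| Protocol 13.3, safety and efficacy | yes | yes | not required |
| SAP 3.5, ST | yes | yes | required |
| SAP 3.5, mITT | yes | yes | required |

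The extra word can matter only for someone who is randomized, dosed and not eligible. A person found ineligible before dosing is already removed by the dosing condition in both documents.

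**Safety: chance of seeing at least one event**

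Inputs from protocol 13.7: 40 participants exposed to mexiletine, event rate 4%, stated probability 80%; for a single dose, rate 8%, with 20 participants from 60 randomized 1:1:1. The formula is P = 1 − (1 − p)^n.

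- Plan's figure: 1 − 0.96^40 = 0.805. Single dose: 1 − 0.92^20 = 0.811. Both reproduce the stated 80%.
- The documents give no number of enrolment errors, so I assume 1, 2 or 4 among the 40 exposed: 1 − 0.96^39 = 0.796; 1 − 0.96^38 = 0.788; 1 − 0.96^36 = 0.770.
- For one dose arm, assuming 1 or 2 lost: 1 − 0.92^19 = 0.795; 1 − 0.92^18 = 0.777.

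An unfavourable single case: if an arm's only serious event falls in the one excluded participant, the table changes from 1/20 (5%) to 0/19.

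**Efficacy: shift in the primary contrast**

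Inputs: planning SD of 5.1 points for the 4-week RMT change (SAP 3.4); 20 per arm; the SAP 3.7.1 contrast, which weights the arms −2, 1, 1 with divisor 2. I approximate the mixed model by a comparison of mean changes.

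- Assume that one excluded participant lies 2 SD from the arm mean: 2 × 5.1 = 10.2 points.
- Shift in that arm's mean: 10.2 / 19 = 0.54 points.
- Shift in the contrast if the participant is in an active arm: 0.54 / 2 = 0.27 points. In the placebo arm the weight is 1, so the shift is 0.54 points.
- Approximate standard error of the contrast: 5.1 × √(1/20 + 1/40) = 1.40. The shifts are 0.27 / 1.40 = 0.19 and 0.54 / 1.40 = 0.39 standard errors.

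The 5.3-point planning effect in SAP 3.4 is for one dose against placebo, so it is not the right yardstick for this pooled contrast.

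**The case against.** The strongest reply is that *eligible* describes a step in enrolment. SAP 2.4 has patients determined to be eligible and then randomized. SAP 2.5 allocates eligible participants. Protocol 6.3 randomizes those who meet all criteria. On that reading SAP 3.5 lists successive steps, and nobody who was dosed is removed. SAP 3.5 contains no procedure for judging eligibility again, which fits this reading. It stands as a plausible meaning, but it makes the word redundant, because *randomized* already implies it. Deleting the word then costs nothing.

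Three further replies also carry weight:

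- **Bias is not shown.** Entry criteria rest mostly on facts from before randomization, and site, coordination and data management staff are blinded (protocol 6.5, SAP 2.7). Exclusion would bias the comparison only if discovery depended on arm or outcome, and the documents suggest no such mechanism.
- **Safety oversight continues.** Serious events go to the coordination center within 24 hours, and the Medical Monitor reviews adverse events monthly (protocol 14.2 and 14.3). What could be lost is their place in the summary tables.
- **Some errors will surface early.** A subject withdrawn before Week 4 may have no post-baseline RMT to exclude.

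A reader might also infer support from two other places, but neither gives any. SAP 2.3 paraphrases entry as "criteria for a diagnosis of sporadic ALS received within 60 months of screening", where protocol 5.2.1 counts from symptom onset. The SAP defers to the protocol for the criteria, so this slip does not change who is in a sample. Central review of TMS and TTNCS tracings (SAP 3.3.1 and 3.3.2) sets quality flags that decide which measurements are used; nothing says that it reopens eligibility.

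**Conclusion.** The point holds as a discrepancy in a governing definition. SAP 3.5 adds a condition that protocol 13.3 and 13.6 do not have, leaves it undefined, and provides no other sample for a dosed participant who fails it. A reader might infer that such participants will certainly disappear from every analysis. The documents do not establish that, because the enrolment-step reading is available and the number of enrolment errors is unknown and may be zero.

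Under the literal reading the numerical effect is small: a loss of about 1 to 3.5 percentage points in the chance of seeing a 4% event, for 1 to 4 exposed participants lost, and about 0.27 points in the primary contrast for one active-arm participant who is a 2-SD outlier. These figures rest on assumed counts and an assumed outlier. The case for change is therefore mainly one of principle: complete safety reporting on everyone exposed, and no exclusion from efficacy after randomization. It should be fixed before unblinding, but it does not undermine the design.

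**What to change.** Delete *eligible* and its comma from both definitions in SAP 3.5. ST then becomes everyone randomized and dosed, by treatment received, and mITT the same people by randomized arm, as in protocol 13.3. Add a count of eligibility deviations by arm to the disposition summary in SAP 3.9.1.

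If an analysis without eligibility violators is wanted, label it supportive, base it only on facts that precede randomization, and have the exclusions decided blind to treatment.

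The cost is one word removed twice and one line added to a table. The downside is slight extra noise in the efficacy estimate from a few ineligible participants.
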